## **4 TREATMENTS**

### **STUDY TREATMENT: CANAGLIFLOZIN**

**Definition of Investigational Product:** A pharmaceutical form of an active substance or placebo being tested or used as a reference in a clinical study, including products already with a marketing authorization but used or assembled (formulated or packaged) in a way different from the authorized form, or used for an unauthorized indication, or when used to gain further information about the authorized form. In this protocol, the investigational product is Canagliflozin.

**Definition of Non-Investigational Product:** Other medications used in the study as support or escape medication for preventative, diagnostic, or therapeutic reasons as components of a given standard of care. In this protocol, the non-investigational products are Metformin, Insulin, GLP-1 agonists, sulfonylureas, and DPP-IV inhibitors. Patients will continue on any combination of the following anti-diabetic therapies: metformin (1-2 grams), insulin, GLP-1 agonists, a DPP-IV inhibitor, or sulfonylureas, as per their study entry dose added to Cana or placebo. As mentioned

before, patients on oral hypoglycemic other than any combination of the following anti-diabetic therapies: metformin (1-2 grams), insulin, GLP-1 agonists, a DPP-IV inhibitor, or sulfonylureas will not be invited to join the study.

This study is being conducted under FDA mandated guideline for use in type 2 diabetes. Though in this particular study Cana is referred to as the investigational drug, it is not a novel drug and we should not need a separate IND for execution of this study.

### **METHOD OF ASSIGNING SUBJECTS TO A TREATMENT**

Subjects, as per selection criteria below will be randomized to treatments using a permuted block design, developed by the Epidemiology & Biostatistics Research Core. This approach ensures groups will be approximately balanced at any time during the study and at study completion. Randomization will be performed by the MFA IDS Pharmacy staff who never come in contact with subjects.

### **SELECTION AND TIMING OF DOSE FOR EACH SUBJECT**

The recommended dose of Cana is 100 mg PO will be given once daily. Cana can be taken with or without food. Cana would preferably be taken in the morning prior to the first meal.

### **DOSE MODIFICATIONS**

No dose modification is necessary prior to CKD stage 3B (eGFR less than 45)

### **BLINDING/ UNBLINDING**

Blinding is critical to the integrity of this clinical study. However, in the event of a medical emergency or pregnancy in a subject, **in which knowledge of the investigational product is critical to the subject's management**, the blind **for that subject** may be broken.

Before breaking the blind of an individual subject's treatment, the investigator should have determined that the information is necessary, i.e., that it will alter the subject's immediate management. In many cases, particularly when the emergency is not investigational product-related, the problem may be properly managed by assuming that the subject is receiving active product without the need for un-blinding.

### **END OF STUDY UNBLINDING PROTOCOL**

Upon completion of the research study, we will undergo the following protocol in order to unblind the research data.

Unblinding is the process by which the allocation code is broken so that the investigator, clinical staff and the trial statistician becomes aware of which intervention each subject enrolled in the research study was taking.

Unblinding at the end of the study is required in order to make unmasked analysis in accordance with the study analysis plan. It is also conducted in order to inform the participants of which investigational product they were assigned to.

#### Time to unblind:

Unblinding shall be conducted when all subjects enrolled in the research study have finished treatment, and all follow up visits. There must be no plan to recruit any more subjects in the research study. Additionally, all data points and outcome measures for each research subject

must have been collected, and ideally compiled. Prior to unblinding there will be a data lock on clinical outcome measures and basic side outcome measures and associated research data collected for the study.

#### Procedure to unblind

Once data (from both the clinical and the basic science side) and has been compiled and is data locked, the investigator can choose to unblind. The Principal Investigator must contact the study sponsor, and receive permission to un-blind. If, for unforeseen reasons, at the pre-determined date for full study unblinding the data analysis on the cellular or basic aspects of the study is lagging behind the clinical data outcome measures (though the data has been acquired) the Principal Investigator in consultation with the study sponsor may choose to un-blind the clinical outcome measures before the basic side data has been analyzed but compiled. Upon confirmation from the study sponsor, the principle investigator must make a written request to the designated party to unblind, hereto referred at the “*unblinder*”. The unblinder is the bio-statistician of the MFA, **[name]**. Upon receipt of an instruction to unblind, the unblinder will sign the request form, indicating their agreement to unblind. This form will then be taken to the pharmacy, **MFA’s IDS**, where a member of the IDS staff will take the form, and will give the unblinding study binder to the unblinder. The pharmacy will sign to indicate their release of the binder, and the unblinder will sign to indicate receipt of the binder. At this point in time the chain of custody of the pharmacy unblended binder has been transferred to the designated party to unblind. The form with all of the signatures will be provided to the study coordinator to be kept in the regulatory binder.

## **5 ADVERSE EVENTS: DEFINITIONS, REPORTING, GUIDANCE**

### **I. Management of Safety Data**

This Study has been designated as an interventional study. Janssen requirements for IIS interventional studies are all adverse events regardless of causality and special situations excluding those from subjects not exposed to a Janssen Medicinal Product and product quality complaints with or without an adverse event will be reported, once the subject has signed and dated an Informed Consent Form is obtained until the subject has completed participation in the study and for 30 days after the last dose of study drug.

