**Sponsor: The George Washington University Medical Faculty Associates**

**Funding Source: Janssen Scientific Affairs, LLC**

## PROTOCOL SYNOPSIS

Protocol Title:	Role of Canagliflozin on gene expression and function of CD34+ endothelial progenitor cells in patients with type 2 diabetes
Site Numbers & Names	GWU Medical Faculty Associates
Research Hypothesis:	Type 2 diabetes is associated with poor stem cell number and function. Poor viability and function of EPCs in diabetes affects the repair and regeneration of the endothelium. We hypothesize that use of Canagliflozin (Cana), along with certain anti-diabetic drugs may help reduce cardiovascular risk by improving EPC survival and function above and beyond adequate glucose metabolism control.
Study Schema: Drugs / Doses / Length of Treatment	
We propose a 2-arm randomized, parallel group, longitudinal study of 16-week intervention duration. The 16-week time interval has been previously shown adequate to observe changes in biochemistry, EPCs and, importantly, pulse wave velocity (PWV) changes. Patients will be randomized to 2 groups:
 
Control (n=20) Concomitant Anti-Diabetic Therapy + Placebo.  Treatment (n=20) Concomitant Anti-Diabetic Therapy + Cana 100mg.

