	
20. Active wounds or recent surgery within 3 months. 21. Untreated hyper/hypothyroidism
 
Additionally, patients who are active smokers, patients who are pregnant, nursing women, and post-menopausal women who are on estrogen hormone replacement therapy (not including oral contraceptives) will be excluded.
 
Detailed Inclusion / exclusion criteria are listed on pages 12-15 of the protocol.

Criteria for Evaluation: (Efficacy, safety, stopping rules, etc.)
	
Subjects will be phone screened to determine initial eligibility. If the phone-screening indicates possible eligibility, then the subjects will come to an in-person screening visit at week -2, then evaluated for end points at weeks 0, 8 and 16. Follow up phone call will be done 30 days after last dose of study drug to assess for adverse effects.
 
Study participation will be stopped for adverse effects at the discretion of the study investigator. Subjects may stop study participation at any time and for any reason.

Statistics:
	
The total sample size is requested, after accounting for attrition over the 16-week period, is 20 subjects per group or 40 subjects total. Sample size estimates were based on the effects of exercise on CD34+/KDR+ cells as described in the literature. The effect of a single session, as well as extended training, on healthy subjects or those with existing cardiovascular conditions appears to increase the CD34+/KDR+ cells.
 
This is a pilot study; as a result appropriate power calculation is not feasible. We however did conduct power analysis, which provided us with 73% power (see statistics section). A p-value of less than 0.05 will be considered statistically significant.

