### **III. Special Situations**

Safety events of interest for a Janssen medicinal product that require expediting reporting and/or safety evaluation include, but are not limited to:

- Drug exposure during pregnancy (maternal and paternal)
- Overdose of a Janssen medicinal product
- Exposure to a Janssen medicinal product from breastfeeding
- Suspected abuse/misuse of a Janssen medicinal product
- Inadvertent or accidental exposure to a Janssen medicinal product
- Any failure of expected pharmacological action (i.e., lack of effect) of a Janssen medicinal product
- Medication error involving a Janssen medicinal product (with or without patient exposure to the Janssen medicinal product, e.g., name confusion)
- Suspected transmission of any infectious agent via a medicinal
- Unexpected therapeutic or clinical benefit from use of a Janssen medicinal product

These safety events may not meet the definition of an adverse event; however, they are treated in the same manner as adverse events. Special situations should be recorded on the Adverse Event page of the CRF.

Any special situation that meets the criteria of a serious adverse event should be recorded on a Serious Adverse Event Report Form and be reported to Janssen Scientific Affairs **within 24 hours of becoming aware of the event.**

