## **V. Reporting Procedures for Adverse Events and Pregnancies [and/or Pregnancies in Partners]**

All adverse events, whether serious or non-serious, related or not related, special situations, pregnancy exposures and/or pregnancies in partners following exposure to a Janssen medicinal product are to be documented by the investigator and recorded in the CRF and in the subject's source records. Investigators must record in the CRF their opinion concerning the relationship of the adverse event to a Janssen medicinal product.

All (serious and non-serious) adverse events reported for a Janssen medicinal product should be followed-up in accordance with clinical practice.

All serious adverse events that have not resolved by the end of the study, or that have not resolved upon discontinuation of the subject's participation in the study, must be followed until any of the following occurs:

- The event resolves
- The event stabilizes
- The event returns to baseline, if a baseline value/status is available
- The event can be attributed to agents other than the study drug or to factors unrelated to study conduct
- It becomes unlikely that any additional information can be obtained (subject or health care practitioner refusal to provide additional information, lost to follow-up after demonstration of due diligence with follow-up efforts)

All serious adverse events, pregnancy exposures and/or pregnancies in partners for Janssen medicinal products under study should be reported directly by the Sponsor Investigator, **within 24 hours of becoming aware**, to Janssen Scientific Affairs using the Janssen Scientific Affairs Serious Adverse Event Report Form. In the event the study is blinded, the Sponsor Investigator will submit an unblinded SAE or pregnancy exposure report to Janssen Scientific Affairs.

All follow-up information for serious adverse events that are not resolved at the end of the study or by the time of patient withdrawal must be reported directly by the Sponsor Investigator, **within 24 hours becoming aware**, to Janssen Scientific Affairs using the Janssen Scientific Affairs Serious Adverse Event Report Form.

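### Reporting to the funder by exposure, and in unblinded form, needs the allocation code while a double-masked trial is running

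*Combined protocol and SAP*

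**What the plan says.** Everything cited is in the combined protocol and SAP.

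- **Scope of reporting (Section 5.I).** The sentence opens "Janssen requirements for IIS interventional studies are all adverse events regardless of causality", adds special situations, and then carves out events, "excluding those from subjects not exposed to a Janssen Medicinal Product". The window starts "once the subject has signed and dated an Informed Consent Form is obtained" and runs to 30 days after the last dose.
- **Speed (Section 5.IX.A).** Serious adverse events and special situations go to the funder within 24 hours of awareness.
- **Form of the report (Section 5.V).** In a blinded study, the sponsor-investigator sends the funder serious-event and pregnancy-exposure reports in unblinded form.
- **Completeness (Section 5.VII).** All safety data are kept in a clinical database. All adverse events, serious or not, are provided in report format, with no limit by exposure.
- **Blinding (Section 4).** An individual code may be broken in a medical emergency or pregnancy, and only if the answer will change how the subject is managed at once. General unblinding waits until every subject has finished treatment and follow-up and the data are locked.
- **Design (Synopsis).** Double-masked and placebo-controlled, with "Control (n=20) Concomitant Anti-Diabetic Therapy + Placebo" and a total of "20 subjects per group or 40 subjects total".
- **Who holds the code (Section 4).** The IDS pharmacy carries out the randomisation, has no contact with subjects, and keeps the unblinding binder.

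**The concern.** A rule that depends on exposure to the active product can be followed only by someone who knows which subjects received it. The plan gives that task, on a 24-hour clock, to the sponsor-investigator, who is meant to be blinded. A second rule has the same person send unblinded reports.

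The stake is the mask. Section 5.V also has investigators record their opinion on whether each event is related to the funder's product, and that opinion is open to influence once the arm is known. Early discontinuation for adverse events is left to investigator judgement as well. Allocation is by permuted blocks, so knowing some assignments narrows the guess for other subjects in the same block; the block size is not stated.

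The second stake is the funder's safety data, which could hold events from one arm only, although another section of the same protocol promises all of them.

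**Working it through.** The plan states no figure on this point, so the check sets the sections side by side.

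**1. Who is excluded?** The inputs are 40 subjects, 20 per group (Synopsis). The excluded share depends on whether matching placebo counts as one of the funder's medicinal products, which the plan does not define.
- If it does not count: 20/40 = 50% of randomised subjects, the entire control arm.
- If it counts: 0/40 of dosed subjects. The exclusion then reaches only people who consented but were never dosed.

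Section 4 does not settle this. Its general definition of an investigational product is "A pharmaceutical form of an active substance or placebo being tested or used as a reference in a clinical study", which takes in placebo, but it then names canagliflozin alone as the investigational product of this protocol.

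**2. Can the exclusion be applied blind?** Not on the first reading. Serious events and special situations have 24 hours (5.IX.A), so whether to report must be decided during the trial, and the decision turns on the arm. The individual code-break condition in Section 4 does not include reporting as a reason, and general unblinding comes after data lock. No section gives a blinded way to do it. Non-serious events have no 24-hour limit, so their filter could wait, but the plan does not say that it will.

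**3. Does the unblinded-report clause solve this?** It gives a route for serious events and pregnancy exposures, but through the blinded person. It applies to such events whether or not any code break is needed for the subject's care, so it is wider than the Section 4 condition. This step does not depend on what placebo counts as.

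**4. Can the blind leak back?** Section 5.X has the funder return a listing of all reported serious events at least quarterly. If only exposed subjects are reported, a subject's presence on that list shows the arm, and so does the absence of an event known to the site.

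**5. Do the reporting sections agree with each other?** No. Section 5.I leaves out unexposed subjects, while 5.VII provides all adverse events. Section 5.I is also awkward internally: its window opens at consent, at the week -2 screening visit, but nobody is dosed before week 0.

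**6. Are the trial's own control-arm data lost?** No.
- The definition in 5.II covers any subject given an investigational or non-investigational product, and control subjects take background anti-diabetic therapy.
- The Section 6 schedule assesses adverse events at weeks 0, 8, 16 and 20 without distinction by arm.
- The Safety Assessments section evaluates events continuously in each patient on study.
- Section 5.VII keeps all safety data.

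The control denominator is therefore 20 randomised, or 20 × (1 − 0.20) = 16 completing at the dropout given in the Introduction. It is not 0.

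**The case against.** **The exclusion may never have been aimed at placebo.** Because the window opens at consent, it may be meant only for screen failures and other undosed subjects. That reading is possible and would remove the conflict in steps 1, 2 and 4. It is not what the text says, since exposure is tied to the funder's product and not to study treatment. It also leaves the unblinded-report clause untouched.

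**The plan already provides for blinded studies.** It does so for serious events and pregnancy exposures. What stands is that a route exists. What fails is its place in the blinded investigator's hands, unreconciled with Section 4.

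**The sentence governs reports to the funder, not what the site collects.** This is correct and limits the point. Three stronger readings are tempting, and the documents do not support them:
- *That no placebo rate remains for safety.* Events are assessed and kept for every patient, as step 6 shows. Section 7 plans no comparison of adverse events by arm, but that gap does not come from the exclusion.
- *That CRF recording is limited to exposed subjects.* Section 5.V contains the words "following exposure to a Janssen medicinal product are to be documented by the investigator and recorded in the CRF", but they close a list that begins with all adverse events and ends with pregnancies in partners. The exposure phrase attaches most naturally to the pregnancy items. At most it is ambiguous.
- *That placebo non-response inflates adverse-event counts because* "Special situations should be recorded on the Adverse Event page of the CRF". The category in 5.III is lack of effect of the funder's product. If placebo is not such a product, placebo non-response is outside it. The section also says that these events may not meet the adverse-event definition.

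**Conclusion.** The point holds as a conflict over blinding and funder reporting, in two parts.

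- **Exclusion by exposure.** If matching placebo is not one of the funder's products, the rule covers 20 of 40 subjects (50%), cannot be applied to serious events and special situations within 24 hours without the code, and contradicts Section 5.VII. If placebo does count, this part disappears. The undefined term makes this an assumption.
- **Unblinded reports by the sponsor-investigator.** This conflicts with the double mask and with Section 4 on either assumption. The number of subjects unblinded would be the number with a serious event or a reported pregnancy exposure. The plan gives no expected rate, so no figure is offered.

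A reader might infer that the trial loses its control-arm adverse-event data. It does not. The exposure is to the blind and to the completeness of the funder's safety data.

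**What to change.** Change the wording in five places.

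1. **Sections 5.I and 5.V.** State that adverse events in all randomised subjects, in both arms, are recorded in the CRF and reported to the funder without reference to allocation, and that any exclusion based on exposure is applied only after end-of-study unblinding.
2. **Section 5.V, unblinded reports.** If the funder requires an unblinded serious-event or pregnancy report, have the IDS pharmacy issue it. The pharmacy already holds the code and has no contact with subjects. The sponsor-investigator sends the blinded report and is not told the arm.
3. **Section 5.X.** Keep allocation out of the reconciliation listing returned to the sponsor-investigator.
4. **Definition.** Say whether matching placebo counts as a product of the funder for reporting purposes.
5. **Reconciliation.** Bring the Section 4 blinding and unblinding text and Sections 5.I, 5.V, 5.VII and 5.IX into agreement on what is sent, when, by whom and in what form.

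The cost is protocol wording and a short pharmacy procedure, with no new visits or data. The downside is that the funder receives a few more event reports.

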### **II. Definitions**

#### **Adverse Event (AE)**

An adverse event is any untoward medical occurrence in a clinical study subject administered a medicinal (investigational or non-investigational) product. An adverse event does not necessarily have a causal relationship with the treatment. An adverse event can therefore be any unfavorable and unintended sign (including an abnormal finding), symptom, or disease temporally associated with the use of a medicinal (investigational or non- investigational) product, whether or not related to that medicinal (investigational or non-investigational) product. (Definition per International Conference on Harmonisation [ICH]).

This includes any occurrence that is new in onset or aggravated in severity or frequency from the baseline condition, or abnormal results of diagnostic procedures, including laboratory test abnormalities.

#### **Adverse Events of Special Interest**

Events that Janssen Scientific Affairs is actively monitoring as a result of a previously identified signal (even if non-serious). These adverse events are:

- Diabetic ketoacidosis (DKA)
- Genital mycotic infection
- Urinary tract infection
- Osmotic diuresis-related AEs
- Volume related AEs

### **Individual Case Safety Report (ICSR)**

A valid ICSR must contain the four minimum criteria required to meet regulatory reporting requirements.

- an identifiable subject (not disclosing the subject's name and address)
- an identifiable reporter (investigational site)
- a Janssen medicinal product
- an adverse event, outcome, or certain special situation

The minimum information required is:

- suspected Janssen product (doses, indication)
- date of therapy (start and end date, if available)
- batch or lot number, if available
- subject details (subject ID and country)
- gender
- age at AE onset
- reporter ID
- adverse event detail (AE verbatim in English), onset date, relatedness, causality, action taken, outcome, (if available)
- Janssen protocol ID

